6.1.2 Secondary Efficacy

Secondary variables of analysis include:

- Achievement of no more than trace ketones in urine post-treatment
- Achievement of no treatment-emergent abnormal value in serum BOHB
- Achievement of no more than trace ketones in urine or treatment-emergent abnormal value in BOHB in serum
- Change from baseline relative to:
 - Time in target glycemic range (70-180 mg/dL);
 - Time in hyperglycemic range
 - Level 1 > 180 mg/dL
 - Level 2 > 250mg/dL
 - Time in hypoglycemic range
 - Level 1 < 70mg/dL
 - Level 2 < 54 mg/dL
- Change from baseline in average daily number of units of bolus insulin dose
- Percent change from baseline in average daily insulin dose
- Achievement of a decrease of at least 0.3% in HbA1c at Week 12 (responders)

Additionally, analysis will be done on hypoglycemia both thresholds (54 mg/dl and 70 mg/dl) using the following variables:

- Change from baseline (2-week period) to Week 12 (2-week period) on the number of hypoglycemia episodes
- Proportion of patients with at least one more treatment-emergent episode of hypoglycemia at Week 12 (2-week period) relative to baseline (2-week period).
- Time-adjusted change from baseline on the number of hypoglycemia episodes.
- Proportion of patients with at least one more time-adjusted treatment-emergent episode of hypoglycemia at Week 12 than at baseline.

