2.3. Parts 1 and 2 (Following 12 weeks of dosing)

Objectives

Primary Objective:

- To evaluate the pharmacodynamic (PD) effect of TTP399 following multiple day dosing (at 12 weeks) in patients with T1DM

Secondary Objectives:

- To evaluate the safety and tolerability of TTP399 administered for 12 weeks in T1DM patients

Exploratory Objectives

- Assess relevancy of non-genomic biomarkers in predicitng responders and efficacy
- To assess changes in patient quality of life

Endpoints (Part 1 and Part 2)

Primary Endpoint:

- Change from baseline in HbA1c at 12 weeks

Secondary Endpoints:

- Change from baseline time in target glycemic range (70-180 mg/dL); hyperglycemic range (Level 1 > 180 mg/dL; Level 2 (>250mg/dL) and hypoglycemic range (Level 1 < 70mg/dL; Level 2 < 54 mg/dL)
- Change from baseline in number of units of insulin (basal, bolus or total daily) dose
- Percent change from baseline in insulin (basal, bolus or total daily) dose
- Achievement of a decrease of at least 0.3% in HbA1c at Week 12 (responders)

Safety Endpoints:

- Adverse events, laboratory, vital sign and electrocardiograms (ECG) parameters

Exploratory Endpoints:

- Plasma (non-genomic) biomarkers
- Diabetes treatment satisfaction questionnaire (s)
- Change from baseline in number of bolus injections of insulin
- An analysis of responders HbA1c < 7% without any severe hypoglycemic events, weight gain, ketoacidosis

Endpoints (Part 1, Interim analysis):

An interim analysis plan that will describe the variables of analysis. Endpoints will include, but not be limited to the following:

Primary Endpoints:

- Change from baseline in bolus insulin (number of units) OR
Change from baseline for time in target glycemic range (70-180 mg/dL)

Secondary Endpoints:

- Change from baseline for time in hyperglycemic range (Level 1 > 180 mg/dL; Level 2 (>250mg/dL) and hypoglycemic range (Level 1 < 70mg/dL; Level 2 < 54 mg/dL)
- Composite endpoint encompassing change from baseline HbA1c and risk of hypoglycemia as described in the SAP
- Change from baseline in average daily glucose

Safety Endpoints:

- Adverse events, laboratory, vital sign and electrocardiograms (ECG) parameters

Exploratory Endpoints:

- Change from baseline in basal or total daily insulin dose (number of units)
- Percent change from baseline in insulin (basal, bolus or total daily) dose
- Change from baseline glycemic markers (fructosamine and 1,5 anhydroglucitol)
- Body weight
- Glycemic variability (mean SD and CoV)

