- To evaluate the safety and tolerability of TTP399 administered for 12 weeks in T1DM patients

Exploratory Objectives

- Assess relevancy of non-genomic biomarkers in predicitng responders and efficacy
- To assess changes in patient quality of life

Endpoints (Part 1 and Part 2)

Primary Endpoint:

- Change from baseline in HbA1c at 12 weeks

Secondary Endpoints:

- Change from baseline time in target glycemic range (70-180 mg/dL); hyperglycemic range (Level 1 $> 180\text{ mg/dL}$; Level 2 $> 250\text{mg/dL}$) and hypoglycemic range (Level 1 $< 70\text{mg/dL}$; Level 2 $< 54\text{ mg/dL}$)
- Change from baseline in number of units of insulin (basal, bolus or total daily) dose
- Percent change from baseline in insulin (basal, bolus or total daily) dose
- Achievement of a decrease of at least 0.3% in HbA1c at Week 12 (responders)

Safety Endpoints:

- Adverse events, laboratory, vital sign and electrocardiograms (ECG) parameters

Exploratory Endpoints:

- Plasma (non-genomic) biomarkers
- Diabetes treatment satisfaction questionnaire (s)
- Change from baseline in number of bolus injections of insulin
- An analysis of responders HbA1c < 7% without any severe hypoglycemic events, weight gain, ketoacidosis

Endpoints (Part 1, Interim analysis):

An interim analysis plan that will describe the variables of analysis. Endpoints will include, but not be limited to the following:

Primary Endpoints:

- Change from baseline in bolus insulin (number of units) OR
Change from baseline for time in target glycemic range (70-180 mg/dL)

Secondary Endpoints:

- Change from baseline for time in hyperglycemic range (Level 1 > 180 mg/dL; Level 2 > 250mg/dL) and hypoglycemic range (Level 1 < 70mg/dL; Level 2 < 54 mg/dL)
- Composite endpoint encompassing change from baseline HbA1c and risk of hypoglycemia as described in the SAP
- Change from baseline in average daily glucose

Safety Endpoints:

- Adverse events, laboratory, vital sign and electrocardiograms (ECG) parameters

Exploratory Endpoints:

- Change from baseline in basal or total daily insulin dose (number of units)
- Percent change from baseline in insulin (basal, bolus or total daily) dose
- Change from baseline glycemic markers (fructosamine and 1,5 anhydroglucitrol)
- Body weight
- Glycemic variability (mean SD and CoV)
- Change from baseline total daily insulin dose
- Percent change from baseline in total daily insulin.

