1.11 Modifications from the Statistical Section of the Protocol

This SAP is consistent with the protocol with the following exceptions:

- The primary analysis is characterized more completely with change based on blinded evaluations and communications with key opinion leaders. Modifications of the statistical analysis that represent departures from the protocol are permitted in an adaptive study, and such changes are explicitly allowed in the protocol.
- A conditional sequence of hypothesis tests has been modified to reflect blinded evaluations and communications with key opinion leaders.

Any other modifications will be documented in amendments to the SAP or the clinical study report.

2 Statistical Hypotheses

The primary objective is to show superiority (using a 2-sided test) of TTP399 to placebo at 12 weeks in patients treated with insulin on a dichotomous variable to delineate patients treated with insulin plus placebo from patients treated with modified insulin with TTP399 added followed by a non-inferiority evaluation of change in HbA1c followed by a superiority evaluation of change in HbA1c .

It is noted that the insulin optimization is applied to all subjects who are not already optimized in the opinion of the investigator. After the start of double-blind study medication, intensive medical monitoring results in modifications of insulin for all patients. Under the alternative hypothesis of treatment benefit, the modification of insulin for subjects on active treatment may be altered as a result of the co-administration of TTP399. Modification of insulin for subjects on placebo is considered standard of care. It is concluded, therefore, that the placebo added to insulin standard of care is the control group for treatment with TTP399 added to a modified regimen of insulin.

The statistical evaluation including non-inferiority evaluation and hypotheses to be tested in Part 2 are as follows:

First Compound Statistical Evaluation (full alpha):

The first evaluation is non-inferiority of treatment with TTP399 800 mg daily plus a modified regimen of insulin and treatment with optimized insulin as determined by the insulin-optimization period of the study, if needed, per protocol:

- Evaluation 1:**

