Noninferiority will be considered to have been established if the 95% confidence interval is completely bounded by the non-inferiority margin of 0.3%, which is specified in the draft guidance: *Guidance for Industry Diabetes Mellitus: Developing Drugs and Therapeutics Biologics for Treatment and Prevention* (CDER; February 2008), Section V.G.1, “Typically we accept a noninferiority margin of 0.3 or 0.4 HbA1c percentage units provided this is no greater than a suitably conservative

estimate of the magnitude of the treatment effect of the active control in previous placebo-controlled trials.”

- The 95% confidence interval will be constructed for the difference between the two treatment groups in mean change in HbA1c to Week 12 using the ANCOVA model as described in the statistical methodology section.
- If the 95% confidence interval is entirely bounded by 0.3% (where a difference of 0.3% reflects the placebo mean is 0.3% better than the mean of the patients treated with TTP399), then the statistical conclusion will follow that treatment with 800 mg TTP399 combined with a modified regimen of insulin is non-inferior to placebo added to insulin following the usual standard of care.

Conditional on the statistical conclusion of non-inferiority of TTP399 relative to placebo, statistical evaluation continued.

It is noted that noninferiority relative to change from baseline in insulin is planned using the confidence interval approach to demonstrate that the maintenance of control of HbA1c achieved during the insulin-optimization period is not driven by an increase in insulin among subjects treated with TTP399. Formal evaluation of this aspect of non-inferiority is not planned, so the statistical evaluation is considered to be nominal rather than rigorous.

The Hochberg method is used for alpha control for Evaluation 2 and Evaluation 3.

- **Evaluation 2:**

Superiority on HbA1c is evaluated:

- H_{01} : The change from baseline in HbA1c at Week 12 for the group treated with 800 mg TTP399 is equal to that of the placebo group.
- H_{11} : The change from baseline in HbA1c at Week 12 for the group treated with 800 mg TTP399 is not equal to that of the placebo group.

- **Evaluation 3:**

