7.6.5 Insulin Device Data

The following data extracted from devices will be of supportive interest:

Mean over the period of

- basal insulin (Prescribed Basal insulin is used)
- bolus insulin
- Number of boluses
- Total insulin (as a measure and adjusted by bodyweight)

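### SAP 6.1.2 narrows the secondary insulin-units endpoint to bolus without declaring it, so the endpoint cannot separate a bolus-to-basal shift from a true reduction

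*SAP*

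**What the plan says.** Protocol 2.3 has two secondary insulin endpoints for Parts 1 and 2. SAP 1.3 repeats both. The first is "Change from baseline in number of units of insulin (basal, bolus or total daily) dose"; the second is "Percent change from baseline in insulin (basal, bolus or total daily) dose".

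The operative list in SAP 6.1.2 differs. Its units variable is "Change from baseline in average daily number of units of bolus insulin dose", and its percent variable is "Percent change from baseline in average daily insulin dose", with no component named.

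SAP 7.6.5 lists means over the period for basal insulin, bolus insulin, number of boluses and total insulin (raw and weight-adjusted), introduced by "The following data extracted from devices will be of supportive interest". It states neither a change from baseline nor a between-arm comparison. For basal it specifies "basal insulin (Prescribed Basal insulin is used"; SAP 8.2 confirms that basal is the prescribed dose and bolus the recorded dose.

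SAP 1.11 opens with "This SAP is consistent with the protocol with the following exceptions". The two exceptions that follow concern the primary analysis and the sequence of hypothesis tests. Neither mentions insulin.

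SAP Section 2 plans a confidence-interval look at change in insulin, to show that maintained HbA1c control "is not driven by an increase in insulin among subjects treated with TTP399". It calls this nominal and names no insulin component and no margin for insulin.

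**The concern.** The protocol lets the SAP supersede it for analyses, so the list in SAP 6.1.2 governs. That list drops two of the three components of the units endpoint and leaves the component of the percent endpoint to be chosen later. The section meant to declare departures from the protocol does not mention it.

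Bolus units on their own are weak evidence on insulin need in this design. Protocol 8.11 has bolus settings changed for every patient on the first day of double-blind dosing. It then has insulin adjusted to fasting and pre-meal targets as well as post-meal targets, with basal settings recorded. Basal can therefore move while bolus moves, and a bolus-only endpoint does not see it.

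At stake is how any claim about insulin use is read. SAP Section 2 wants to say that HbA1c control was not bought with more insulin. That is a statement about all insulin, and the only units variable kept at secondary level covers part of it.

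**Working it through.** The plan gives no figure on this point to reproduce. The check is a comparison of texts, followed by arithmetic to show what the endpoint can and cannot detect.

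**1. Status of each variable**

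| Variable | Protocol 2.3 and SAP 1.3 | SAP 6.1.2 | SAP 7.6.5 |
|---|---|---|---|
| Bolus, units | secondary | secondary | period mean, supportive |
| Basal, units | secondary | absent | period mean, supportive (prescribed dose) |
| Total daily, units | secondary | absent | period mean, supportive (raw and weight-adjusted) |
| Percent change | secondary; three components named | secondary; component not named | not listed |

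SAP 6.1.2 therefore conflicts with both the protocol and SAP 1.3, and SAP 1.11 does not record the difference.

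**2. What bolus units can distinguish**

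The documents give no baseline insulin doses, so these inputs are assumptions: total T = 50 U/day, bolus share s = 40-60%, proportional fall in bolus c = 10-30%, and fraction m of that fall that reappears as basal.

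- Bolus change = -T x s x c. Lowest: 50 x 0.40 x 0.10 = 2.0, so -2.0 U/day. Highest: 50 x 0.60 x 0.30 = 9.0, so -9.0 U/day. The fraction m does not enter.
- Percent change in total = -(1 - m) x s x c.

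| Fraction moved to basal | Bolus-units endpoint | Change in total daily insulin |
|---|---|---|
| m = 1 (pure shift) | -2 to -9 U/day | 0% |
| m = 0.5 | -2 to -9 U/day | -2% to -9% |
| m = 0 (pure saving) | -2 to -9 U/day | -4% to -18% |

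The endpoint column is the same in all three rows. Only total insulin, or basal beside bolus, separates them.

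**3. What the percent-change variable adds**

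If it means total daily insulin, it gives the last column above and does separate the cases. If it means bolus, it reads -10% to -30% in all three rows and adds nothing. The SAP does not say which.

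**4. The Day 1 instruction**

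Protocol 8.11 raises the insulin-to-carbohydrate ratio by 10-30%, usually 20%. The carbohydrate bolus is carbohydrate divided by this ratio, so a rise of r lowers it by 1 - 1/(1 + r):

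- r = 10%: 1 - 1/1.1 = 9.1%
- r = 20%: 1 - 1/1.2 = 16.7%
- r = 30%: 1 - 1/1.3 = 23.1%

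This applies in both arms under blinding. SAP 8.1 takes the insulin baseline from the placebo run-in, before this step, and protocol 8.11 allows run-in insulin changes only for safety. A change from baseline in bolus units within one arm therefore includes a cut that the protocol imposed. Later titration may reverse some or all of it, so its size at Week 12 is unknown. SAP 7.6.2 plans one-sample t and Wilcoxon tests within each group for continuous secondary measures. On bolus units these can show a fall by design in either arm. The between-arm contrast does not have this problem.

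**The case against.** The strongest reply is that basal and total insulin do not disappear. The preceding bullet in SAP 6.1.2 says bolus when it means bolus, so the percent-change bullet most naturally means all insulin. SAP 7.6.5 summarises basal and total, and SAP Section 11 lists a summary of insulin usage. SAP Section 2 refers to insulin, not bolus, and labels its check nominal. No insulin variable is in Evaluations 1 to 7, so no alpha and no success criterion depends on it. All of this stands, and it limits the point.

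There is also a case for bolus. The protocol synopsis asks whether the drug can replace or reduce mealtime bolus, bolus units are one of the interim primary variables, and bolus is the component taken from recorded doses. That would justify a declared focus on bolus. It does not explain why the change goes undeclared.

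On disclosure, the protocol's wording joins the components with an or, protocol 10.6.1 leaves other variables to the SAP, and SAP 1.11 is headed for the protocol's statistical section, whereas these endpoints sit in protocol 2.3. SAP 1.11 also allows other changes to be documented later. This softens the omission. However, documentation only in the study report would not be pre-specification, and SAP 1.3 still lists the wider endpoints.

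Three stronger readings are tempting and are not supported:

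- A reader might infer that a bolus-to-basal shift will be reported as insulin-sparing. Nothing in the documents says so, and total insulin will be on display.
- A reader might infer that bolus was chosen because it would look best. The documents give no evidence of that, and do give a scientific reason for interest in bolus.
- A reader might infer that the Day 1 cut biases the treatment comparison. It is applied to both blinded arms and affects only the within-group tests.

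**Conclusion.** The point holds as a gap in specification and disclosure. SAP 6.1.2 limits the units endpoint to bolus and leaves the percent endpoint undefined, against protocol 2.3 and SAP 1.3 and without an entry in SAP 1.11. Taken alone, the units endpoint cannot distinguish a shift from a reduction, and it cannot carry the SAP Section 2 statement about insulin.

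The size is modest. The primary analysis, the test hierarchy and the alpha are untouched, and the data needed to see a shift are already planned as supportive output. The -2 to -9 U/day illustration rests on the assumed 50 U/day, bolus share and bolus fall. It shows what the endpoint cannot detect and does not predict that a shift will occur, or will occur more in one arm. The comparison of texts needs no assumption.

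**What to change.** In SAP 6.1.2, restore change from baseline in units for basal and total daily insulin as secondary variables beside bolus, and define the percent-change variable as total daily insulin. In SAP Section 2, name between-arm change in total daily insulin as the variable for the nominal check. Report bolus next to basal and total, and rest the reading of bolus on the between-arm contrast and not on the within-group tests of SAP 7.6.2. If the narrowing to bolus is deliberate, list it with its reason in SAP 1.11.

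The cost is SAP wording and a few more secondary analyses outside the alpha hierarchy; SAP 7.6.5 already plans to extract the data. There is one real drawback. Total daily insulin adds prescribed basal to recorded bolus (SAP 7.6.5 and 8.2), so basal changes that were not prescribed would be missed. That limitation should be stated beside the result.

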6.1.3 Tertiary and Exploratory Efficacy

- Standard deviation of daily CGM and associated CV%
- Plasma (non-genomic) biomarkers
- Diabetes treatment satisfaction questionnaire (s)
- Change from baseline in number of bolus injections of insulin
- An analysis of responders HbA1c < 7% without any severe hypoglycemic events, weight gain, diabetic ketoacidosis

Additionally, a quality of life (Likert Scale) question is classified as an exploratory variable of interest: At Week 12, the patient should be asked to respond to the following QOL question with one of the answers below. The answer will be entered in the EDC.

Question: “How is your quality of life relative to study start?”

Answers (choose one): markedly worse, moderately worse, slightly worse, no change, slightly improved, moderately improved, markedly improved.

The Diabetes Treatment Satisfaction Questionnaire status version (DTSQs) is completed at Screening and Week 12, and the Diabetes Treatment Satisfaction Questionnaire change version (DTSQc) is completed at the Week 12 visit. These questionnaires will be evaluated as exploratory variables of analysis in this Part.

6.2 Safety Variables

Safety is monitored in this study by collection of adverse events, vital signs, electrocardiography, and clinical laboratory measures with intensive medical monitoring for evidence of DKA or important hypoglycemic events. It is noted that all untoward events or experiences are reported as adverse events regardless of whether they are identified by clinical observation, patient reporting, physical examination, clinical laboratory test result, electrocardiography, or any other examination or test. It is noted that listings are reviewed by medically qualified individuals of vital signs, laboratory

data, electrocardiograms (ECG), and all safety data to ensure that safety signals are identified and reported in the analysis of the safety data from this study.

6.2.1 Treatment-emergent Adverse Events

A treatment-emergent adverse event (TEAE) is one that was not present at before the first dose of study medication in each period or represents the exacerbation of a pre-existing condition. It is noted that AEs that emerge during the placebo-run-in phase will be captured and reported separately from AEs that emerge during the double-blind-treatment period.

Safety variables of analysis include description of the following:

- Patients with TEAEs by Preferred Term (PT)
- Patients with TEAEs by system organ class (SOC) and PT within SOC
- Patients with any hypoglycemic TEAE by PT
- Patients with any severe TEAE
- Patients with any serious TEAE
- Patients with any related TEAE
- Patients with TEAEs that result in termination from the study

6.2.2 Vital Signs

Vital Signs variables of analysis include raw means and mean changes from baseline for the vital signs measured in this study:

- Sitting pulse rate
- Sitting systolic and diastolic blood pressures
- Bodyweight

6.2.3 Clinical laboratory assessments

Clinical laboratory variables of analysis include raw means and mean changes from baseline for the clinical laboratory measures in this study

- Hematology: hemoglobin, hematocrit, RBC count, platelet count, WBC count, total neutrophils (abs), eosinophils (abs), monocytes (abs), basophils (abs), lymphocytes (abs)
- Clinical chemistry: BUN, creatinine, calcium (total), sodium, potassium, chloride, total carbon dioxide, (bicarbonate), AST (SGOT), ALT (SGPT), alkaline phosphatase (ALK), total bilirubin, direct (conjugated) bilirubin, uric acid, albumin, total protein
- Lipid panel: total cholesterol, HDL-C, LDL-C, triglycerides
- Specialty laboratory tests: HbA1c, C-peptide, lactate, ketones, free fatty acids, GGT, fructosamine, glucagon, 1, 5 anhydroglucitrol.

A treatment-emergent abnormal value (TEAV) is a laboratory analyte that is abnormal after administration of study medication that was not present prior to the administration of study medication.

Safety variables of analysis include:

- Proportions of patients with TEAVs
- Proportions of patients with a TEAV in any liver function test (LFT) including ALT, AST, total bilirubin, alkaline phosphatase.

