9.8.4. Potential Cases of Drug Induced Liver Injury

Abnormal values in aspartate transaminase (AST) and/or alanine transaminase (ALT) concurrent with abnormal elevations in total bilirubin that meet the criteria outlined below, in the absence of other causes of liver injury, are considered potential cases of drug-induced liver injury. (These events should be considered important medical events and reported as serious adverse events.)

Participants who present with the following laboratory abnormalities should be evaluated further to definitively determine the etiology of the abnormal laboratory values:

- a. Participants with AST or ALT baseline values within the normal range who subsequently present with AST or ALT ≥ 3 times the upper limit of normal with a total bilirubin ≥ 2 times the upper limit of normal with no evidence of 1) hemolysis, 2) cholestasis (elevated alkaline phosphatase ≥ 2 times the upper limit of normal or not available) or 3) Gilbert's Syndrome (common benign condition associated with intermittent elevations of primarily indirect, unconjugated, bilirubin to approximately 2 \times upper limit of normal (ULN)).
- b. Participants with pre-existing AST or ALT baseline values above the normal range who subsequently present with AST or ALT ≥ 2 times the baseline values and ≥ 3

times the upper limit of normal with a total bilirubin \geq 2 times the upper limit of normal with no evidence of 1) hemolysis, 2) cholestasis (elevated alkaline phosphatase \geq 2 times the upper limit of normal or not available) or 3) Gilbert's Syndrome (common benign condition associated with intermittent elevations of primarily indirect, unconjugated, bilirubin to approximately 2 x upper limit of normal (ULN)).

Increases defined above should be confirmed with repeat testing within 48 to 72 hours. In addition to repeating AST and ALT, additional laboratory tests should include albumin, amylase, creatine kinase, total bilirubin, direct and indirect bilirubin, gamma-glutamyl transferase (GGT), international normalized ratio (INR) and alkaline phosphatase. Symptoms should be assessed.

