10.7.1. Safety Variables of Analysis

Adverse Events

Definitions:

- A *treatment-emergent adverse event* (TEAE) is an event that is observed or reported after administration of study medication that was not present prior to study medication administration or an event that represents the exacerbation of a pre-existing event.
- An *adverse withdrawal* is a patient who withdrew from the study due to an adverse event.
- A *serious adverse event* (SAE) is an AE that is classified as serious according to the criteria specified in the study protocol.

Adverse events variables of analysis include:

- Proportions of patients with TEAEs by Preferred Term and decreasing frequency of TEAE
- Proportions of patients with TEAEs by System Organ Class (SOC) and Preferred Term
- Proportions of patients with adverse withdrawals

Vital Signs

Vitals signs measures of blood pressure and pulse will include the following variables of analysis:

- Mean values and mean changes of values from Baseline to Visit
- Proportions of patients with potentially clinically significant abnormal values or changes in vital signs measures.
- Proportions of patients with AEs related to vital signs

Clinical Laboratory

Clinical Laboratory hematology and clinical chemistry variables of analysis include:

- Proportions of patients with TEAVs (shifts from normal status to abnormal status)

Proportions of patients meeting DILI criteria per FDA Guidance for Industry
“Drug-induced liver injury: premarketing clinical evaluation” (CDER, CBER, July 2009)

- Means and mean changes from Baseline to Visit
- Proportions of patients with new (post Baseline) potentially clinically significant values (Clinical laboratory-related AEs) or changes in laboratory values

Electrocardiography

Electrocardiography variables of analyses will include:

- Proportion of patients with Corrections to QT intervals will be made by Bazett’s method and also by Fridericia’s method. Categorical analysis will be done consistent with ICH E14, “Clinical evaluation of QT/QTc interval prolongation and proarrhythmic potential for non-antiarrhythmic drugs” (October 2005).
- Means and mean changes from Baseline to Visit
- Proportions of patients with new (post Baseline) potentially clinically significant values (Clinical laboratory-related AEs) or changes in laboratory values

Statistical Methodology for Safety Analysis

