7.7.4 Clinical Laboratory Measurements

Because “exacerbations” of pre-existing abnormalities in laboratory analytes are examined using clinical judgment and are reported as TEAEs, additional analysis on TEAVs is limited to subjects with values that are normal prior to dosing and abnormal after dosing.

Adverse events of special interest also treatment-emergent abnormal values (TEAVs) in laboratory parameters related to liver function tests, specifically ALT, AST, bilirubin, and ALK.

Potentially clinically significant values in laboratory analytes will be examined in accordance with the table of values or changes of potential clinical significance in this SAP. Proportions of subjects in each treatment group who meet the criteria will be analyzed.

Laboratory data will be summarized by Baseline and change from Baseline to each scheduled assessment time with descriptive statistics.

Liver function tests have additional monitoring for this study.

To explore the potential for drug-induced liver injury consistent with *Guidance for Industry “Drug-induced liver injury: premarketing clinical evaluation”* (CDER, CBER, July 2009), subjects will be summarized and listed who meet the following criteria:

- (1) Elevations in either AST or ALT of at least 3-times the upper limit of normal, and

- (2) An accompanying abnormal bilirubin.

Additionally, a summary and listing will be examined for subjects with elevations in either AST or ALT of at least 3-times the upper limit of normal, regardless of bilirubin.

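### The liver-test TEAV proportion has no direction, so values that fall below range count as a liver signal; separately, the SAP's liver-injury summary uses a looser bilirubin rule than protocol 9.8.4.

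*SAP*

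**What the plan says.** **TEAV rule.** SAP 6.2.3 states: "A treatment-emergent abnormal value (TEAV) is a laboratory analyte that is abnormal after administration of study medication" and was not so before dosing. SAP 7.7.4 adds that "additional analysis on TEAVs is limited to subjects with values that are normal prior to dosing and abnormal after dosing". Protocol 10.7.1 has the same idea: "Proportions of patients with TEAVs (shifts from normal status to abnormal status". None of the three gives a direction.

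**Where it is applied to the liver.** SAP 6.2.3 lists "Proportions of patients with a TEAV in any liver function test (LFT) including ALT, AST, total bilirubin, alkaline phosphatase" as a safety variable. SAP 7.7.4 places these TEAVs with the adverse events of special interest, "specifically ALT, AST, bilirubin, and ALK".

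**Liver-injury summary.** SAP 7.7.4 requires two things together: "Elevations in either AST or ALT of at least 3-times the upper limit of normal, and" then "An accompanying abnormal bilirubin". It also summarises and lists everyone who reaches the AST/ALT limit, whatever the bilirubin.

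**Protocol case definition.** Protocol 9.8.4 pairs AST or ALT at 3 or more "times the upper limit of normal with a total bilirubin" of at least 2 x ULN. It requires no evidence of hemolysis, cholestasis or Gilbert's syndrome. When baseline AST or ALT is already raised, it also requires at least twice the baseline value.

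**Table of clinical concern** (SAP section 14, protocol Appendix 3). ALT, AST and alkaline phosphatase above 3 x ULN; total bilirubin above 2.5 x ULN. All are upward only.

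**The concern.** A programmer who follows the TEAV text will flag every out-of-range value, low or high. For ALT, AST, alkaline phosphatase and bilirubin the question of interest is elevation. Elsewhere the SAP writes the direction down: the responder criteria in 6.1.1 require beta-hydroxybutyrate and lactic acid not to rise above the reference range, and the aminotransferase limb of the liver-injury summary speaks of elevations.

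TTP399 is a liver-selective glucokinase activator, so the liver table will be read closely. Low values add background in both arms. If the drug pushes values up, it also removes low values from the active arm while placebo keeps them, so the contrast between arms narrows.

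The bilirubin wording raises a smaller issue. The table offered as the liver-injury summary can contain patients who are not cases under protocol 9.8.4. SAP 1.11 says the SAP is consistent with the protocol apart from the primary analysis and the test sequence, so this difference is undeclared.

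**Working it through.** The documents state no rate, power or sample size for either liver output, so there is no figure of theirs to reproduce. The check is a reading of the rules plus an illustration.

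**1. The rules side by side**

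| Rule | Tests | Direction | Limit |
|---|---|---|---|
| Liver-test TEAV (SAP 6.2.3, 7.7.4) | ALT, AST, bilirubin, ALP | none stated | reference range |
| SAP liver-injury summary, limb 1 | AST or ALT | up | at least 3 x ULN |
| SAP liver-injury summary, limb 2 | bilirubin | none stated | any abnormal |
| Protocol 9.8.4 | AST or ALT, with bilirubin | up | at least 3 x ULN and at least 2 x ULN, with exclusions |
| Table of clinical concern | all four | up | above 3 x ULN (bilirubin above 2.5 x ULN) |

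The TEAV rule is undirected for all four tests. In the liver-injury summary only the bilirubin limb is undirected.

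**2. Simple bounds on the TEAV proportion**

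Inputs from the documents: 4 tests, and chemistry panels at Weeks 2, 6 and 12 on treatment (protocol Appendix 2, Part 2). SAP 7.1 sets the follow-up visit aside. Assumed: 2.5% of values lie above range, a fraction L lies below, the patient is normal on all four tests before dosing, and there is no drug effect. Then P(at least one TEAV) = 1 - (1 - p)^k, with k = 12 if visits are independent and k = 4 if the three visits act as one.

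- Highs only, p = 0.025: 1 - 0.975^12 = 26.2%; 1 - 0.975^4 = 9.6%.
- As written, L = 1%, p = 0.035: 1 - 0.965^12 = 34.8%; 1 - 0.965^4 = 13.3%.
- As written, L = 2.5%, p = 0.05: 1 - 0.95^12 = 46.0%; 1 - 0.95^4 = 18.5%.
- As written, L = 0: the same as highs only.

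**3. Model with correlated visits**

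Each test follows a normal random-intercept model in SD units; the four tests are independent; a TEAV needs a normal baseline and at least one of three on-treatment values out of range; 400,000 simulated patients per case. The upper limit is +1.96 and the lower limit is set by L. Within-patient correlation 0.7:

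| Low tail L | As written, no effect | As written, +0.5 SD | Difference (points) |
|---|---|---|---|
| no lower limit | 15.1% | 40.6% | 25.5 |
| 1% | 21.5% | 41.6% | 20.1 |
| 2.5% | 28.5% | 42.9% | 14.4 |

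Counting highs only gives about 15.1% with no effect and about 40.5% with the shift, a difference of about 25 points, for every L.

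At correlation 0.5, the no-effect rate is 19.5% highs-only, against 27.2% (L = 1%) and 36.0% (L = 2.5%) as written. At correlation 0.8 it is about 12.2%, against 17.5% and 23.3%.

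With the 45 patients per arm planned in SAP 1.7 and correlation 0.7, the no-effect counts are 45 x 0.151 = 6.8 highs-only, 45 x 0.215 = 9.7 (L = 1%) and 45 x 0.285 = 12.8 (L = 2.5%).

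**4. Bilirubin limb**

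Any bilirubin of at least 2 x ULN is abnormal, and both documents use 3 x ULN for AST/ALT. Every protocol 9.8.4 case therefore meets the SAP screen. The SAP screen can add patients with bilirubin between 1 and 2 x ULN, patients with an excluding condition, patients whose raised baseline AST/ALT has not doubled and, read literally, patients with a low bilirubin.

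**The case against.** The strongest reply is that a rise would not be hidden. The SAP also reports mean change from baseline by visit for these analytes, upward-only thresholds with proportions by arm, the list of AST/ALT at 3 x ULN or more regardless of bilirubin, change to maximum, and a TEAV listing. No hypothesis in SAP section 2 uses the TEAV proportion. This stands, and it limits the harm. It does not make the TEAV proportion right: the thresholds start at 3 x ULN (2.5 x ULN for bilirubin), so among the planned proportions the TEAV one is the summary for milder rises.

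It is also fair to say that the size rests on an input nobody can read from the documents. If the laboratory sets no lower limits for these tests, the two rules coincide. The model also treats ALT and AST as independent, which they are unlikely to be.

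On bilirubin, the broader screen is the cautious direction, and protocol 9.8.4 is written for work-up and serious-event reporting rather than for a table. Both points stand. What remains is an undirected word and an undeclared difference.

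A reader might infer that the liver-injury summary itself counts low ALT, AST or alkaline phosphatase. It does not: it needs AST or ALT at 3 x ULN or more, and alkaline phosphatase is not part of it. A reader might also infer that the looser bilirubin rule loses protocol cases. It cannot, as step 4 of the check shows.

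**Conclusion.** The point holds for the TEAV rule. As written, the special-interest liver-test proportion counts values below range. With correlation 0.7, three visits and four independent tests, the no-effect rate runs from 15% (no lower limit) through 21.5% (1% low tail) to 28.5% (2.5% low tail), against 15% highs-only. A 0.5 SD rise gives a difference between about 25 and about 14 to 15 points, against about 25. A near-doubling of background is the top of this range. It should not be quoted as the expected effect, because the documents give no reference ranges.

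The bilirubin mismatch is secondary. The SAP and protocol definitions differ and SAP 1.11 does not say so, but the consequence is extra patients in the table and unclear labelling, not missed cases.

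**What to change.** 1. In SAP 6.2.3 and 7.7.4, define a liver-test TEAV for ALT, AST, total bilirubin and alkaline phosphatase as normal before dosing and above ULN after dosing. Other analytes can keep the two-sided rule.
2. In the SAP 7.7.4 liver-injury summary, reconcile the bilirubin limb with protocol 9.8.4. At minimum, state that abnormal means above ULN, label the table as a broad screen, and report beside it the subset that meets the full protocol 9.8.4 definition, including its exclusions and its raised-baseline condition.
3. Declare the broader screen in SAP 1.11, and label the 2 x ULN and 2.5 x ULN bilirubin limits by purpose.

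Cost: a few lines of SAP text, one condition in the TEAV program and one extra line in the liver-injury table. No new data are needed: the laboratory values are already collected, and protocol 9.8.4 already asks for the work-up behind its exclusions.
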